### **Measurement of Efficacy Results**

A total of 70 participants who met the research criteria were asked to visit the clinic once every 1 week (0th, 1st, 2nd, 3rd, and 4th/last week of the study period) with a total of 5 clinical visits including initial examination. During each visit, the use of the supplement is currently reviewed and symptoms or side effects are noted. During screening visits, demographic and lifestyle information is collected (age, alcohol consumption, and smoking habits). Medical history is taken and urine turbidity tests are carried out.

The following parameters are assessed; Weight, Height, WHR and BMI during each visit. Blood samples were collected after a minimum of 12 hours of fasting during initial screening as

well as in the 0, 2nd and 4th weeks of the intervention period to obtain blood glucose profiles, total cholesterol, triglycerides, high-density lipoprotein (HDL), low-density lipoprotein (LDL) and PGC-1 $\alpha$ . Blood samples were taken from the arm vein. The arm vein to be punctured is cleaned with 70% alcohol and allowed to dry. A tourniquet is placed on the upper arm to expose and slightly accentuate the veins. The skin is stretched over the vein with the fingers of the left hand so that the vein cannot move. The skin is pierced with a needle and syringe with the right hand until the tip of the needle enters the lumen of the vein. The tourniquet is removed and slowly withdraw the syringe suction until the desired amount of blood is obtained. A 70% alcohol swab is placed over the needle and the syringe and needle are removed. The needle is removed from the syringe and the blood sample is transferred into a vacutainer tube. The sample is then centrifuged for 20 minutes at a speed of 3000 rpm. Finally, the serum is collected for analysis of blood glucose, total cholesterol, triglycerides, high-density lipoprotein (HDL), low-density lipoprotein (LDL) and PGC-1 $\alpha$ . Blood glucose, triglycerides, high-density lipoprotein (HDL), low-density lipoprotein (LDL) and cholesterol levels were tested using COBAS Integra® 400 plus analyzer (Roche). The sample was washed with Phosphate Buffered Saline (PBS, pH 7.4) 1% until the liquid was clear. The sample was centrifuged at 3000 rpm for 20 minutes to obtain pellets and supernatants. The supernatant is taken for PGC-1 $\alpha$  examination. The concentration of PGC-1 $\alpha$  is measured using the Human PGC-1 $\alpha$  (PGC1 alpha (PPARGC1A) (NM\_013261) Human Untagged Clone kit.

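### The PGC-1α procedure leaves the serum dilution unknown and names no identifiable quantitative assay, so the reported concentration cannot be interpreted as written

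*Combined protocol and SAP*

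**What the plan says.** The Introduction names blood glucose, total cholesterol and PGC-1 as the outcomes of interest; none is designated primary.

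Measurement of Efficacy Results schedules fasting blood draws at screening and at three later points ("well as in the 0, 2nd and 4th weeks of the intervention period"). After the first spin it states: "Finally, the serum is collected for analysis of blood glucose, total cholesterol, triglycerides", and the list goes on to HDL, LDL and PGC-1α. Glucose and the four lipid measures are then assigned to a named COBAS analyser.

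PGC-1α alone follows a further route. "The sample was washed with Phosphate Buffered Saline (PBS, pH 7.4) 1% until the liquid was clear". A second spin comes next: "The sample was centrifuged at 3000 rpm for 20 minutes to obtain pellets and supernatants". The PGC-1α test uses the fluid above the pellet, and the concentration is said to be measured with a product that carries a gene name, an accession number and the description "Human Untagged Clone kit".

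Statistical Analysis specifies fixed effects for group, visit and their interaction. It says nothing about assay error or dilution.

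**The concern.** A concentration can be interpreted only if the reader knows what material was measured, how far it was diluted and by what assay. Here the wash has a visual end point. Followed exactly, it permits a different volume of buffer for each specimen, and nothing tells the reader to record that volume or correct for it. This is more than a missing detail, because the stated rule itself leaves the dilution open.

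The product description does not identify a quantitative assay: there is no detection principle, calibrator, unit, range or precision.

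At stake is the meaning of one of the three aim outcomes. Its absolute level could not be read as a serum value or compared with other data, and its group-by-visit comparison may carry avoidable noise.

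**Working it through.** The plan gives no PGC-1α value, SD, dilution or assay precision, so there is no figure to reproduce. The check is a reading of the text, a count, and some algebra on what an unknown dilution does.

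**1. Specimen.** Serum is the only material that the documents assign to PGC-1α, so the sample that is washed is most naturally that serum. The text does not say so. Washing to clarity and then separating a pellet also fits poorly with serum already taken off by centrifugation. The ambiguity is real, but the serum reading is the leading one.

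**2. Wash.** No starting volume, buffer volume, number of washes or back-correction is stated. The one figure, 1%, could be a buffer strength or a proportion; the text does not explain it.

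**3. Assay.** Six analytes are listed and five go to the COBAS analyser, which leaves 6 − 5 = 1, PGC-1α. No other section supplies its assay. The ELISA reader under Antioxidant Test on Sea Grape Extract serves the DPPH test of the extract.

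**4. Specimens affected.** 70 randomised men × 3 draws (weeks 0, 2 and 4) = 210, with full attendance assumed. Screening draws are left out: they lie outside the comparison, and the text does not settle whether screening is separate from week 0.

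**5. Effect on the absolute level.** Let c be the true serum concentration and 1:k the ratio of serum to PBS. Without back-correction, reported value = c/(1 + k). For assumed k of 0.5, 1, 2, 5 and 9, this is 67%, 50%, 33%, 17% and 10% of c. These ratios are illustrations and do not come from the documents. They show that the level is undetermined until k is known.

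**6. Constant dilution.** If k is the same for every specimen:
- ratio of arms: [c₁/(1 + k)] / [c₂/(1 + k)] = c₁/c₂;
- standardised difference: [(m₁ − m₂)/(1 + k)] / [SD/(1 + k)] = (m₁ − m₂)/SD.

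Both are unchanged.

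**7. Varying dilution.** On the log scale, log(reported) = log(c) − log(1 + k). Suppose log(1 + k) varies between specimens with SD s, independently of arm and visit.
- Variance added to one man's change from week 0 to week 4: 2s².
- Variance added to the difference between two arms of 35: 2s² × (1/35 + 1/35) = 4s²/35.
- SE from dilution alone: s × √(4/35) = 0.338 s.

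The expected difference does not move; only its precision suffers. The documents give neither s, nor the between-man SD of PGC-1α, nor a target difference. The loss of precision or power therefore cannot be computed.

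**The case against.** The best defence is that this is a reporting gap. Serum is plainly assigned to PGC-1α, a concentration is said to be measured with a named kit, and the odd product name may be a slip. The trial is randomised and double-blind, so uniform handling would leave the group comparison sound, and the other two aim outcomes are untouched. Most of this stands. It limits the point to interpretability and possible noise, and it lowers the severity. It does not supply a dilution factor, and a corrected kit name would still leave the wash-until-clear rule in place.

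Four stronger readings are tempting, and the documents support none of them:
- **The laboratory had no valid assay.** The text fails to identify one. Whether the product was miscited cannot be settled from it.
- **The assayed material was not serum.** No section says that clot, cells or tissue was collected for PGC-1α.
- **The result is biased between arms.** That would need dilution to differ systematically by arm, and nothing shows this.
- **The whole blood panel is suspect.** The wash is tied to PGC-1α only, and the other five analytes have a named analyser.

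**Conclusion.** The point holds in limited form. As written, the procedure leaves the PGC-1α dilution unknown and possibly different from specimen to specimen, and no quantitative assay can be identified from the text. The absolute serum concentration cannot be interpreted, and noise may be added to the group-by-visit comparison. Relative group differences survive if the dilution was constant and the assay valid.

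The scope is one of three aim outcomes and 210 scheduled specimens. This rests on the serum reading of the washed sample and on full attendance. The size of the error is unknown and cannot be derived from the documents. The severity is one level below must-fix: the text needs correcting, but neither bias nor an invalid assay has been shown.

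**What to change.** 1. From laboratory records, establish which specimen was washed, the wash volume, what 1% means and which assay product was used. Correct the PGC-1α text in Measurement of Efficacy Results accordingly.
2. For samples not yet processed, replace washing to visual clarity with either no wash or one fixed, recorded dilution that is multiplied back, as the named assay requires. Name a calibrated quantitative assay and its units.
3. For samples already processed, where the dilution or the assay cannot be established, do not report the values as serum PGC-1α concentrations. Report relative between-group results only if a valid assay and a constant dilution are confirmed.

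The cost is a records check and one rewritten paragraph. Only if no quantitative assay was in fact used does a kit have to be bought for up to 210 specimens. Re-assay would also need retained serum, and the plan does not say whether any was kept.

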### **Evaluation of Safety and Diet**

The safety of the extract is assessed by the following procedure. Urine Test Strips 10 Verify Parameters, Parameters examined are:

- Glucose (50 -100 mg / dl)
- Protein (7.5 - 15 mg / dl)

- pH (5-9)
- Leukocytes (9-15 leu / ul)
- Nitrite (0.05-0.1 mg/ dl)
- Urobilinogen (0.2-1.0 mg / dl)
- Blood (5-10 Ery/ul)
- Ketones (2.5-5 mg/dl)
- Bilirubin (0.4-1.0 mg/ dl)
- Specific Gravity (SG) (1,000-1,030)

Test the urine parameters above using *Urinalysis 10U Reagent Strips Verify* (REF U031-102 exp. 2022-03-05). Pulse rate and blood pressure are measured on each visit after a 5-minute break using intelliVue MP70 (Philips, Netherlands). Personal reports are also recorded at these times. We kept the subjects maintaining their usual diet and activity, and all participants completed diet records on each visit to the clinic during the intervention period to evaluate their energy intake and diet quality. Food intake data were analyzed by a nutritionist ([name], S.Gz).

### **Statistical Analysis**

Statistical analysis is performed using SPSS software, version 26 (IBM Corporation). Fixed effects include treatment groups, treatment visits, and interactions between treatment and visit groups. The value  $p < 0.05$  is considered statistically significant.

Table 1. Dose Conversion of Experimental Animals with Humans

	Mice 20 g	Rat 200 g	Guinea Pig 400 g	Rabbit 1,5 kg	Cat 2 kg	Ape 4 kg	Dog 12 kg	Human 70 kg
Mice 20 g	1,0	7,0	12,25	27,8	29,7	64,1	124,2	387,9
Rat 200 g	0,14	1,0	1,74	3,9	4,2	9,2	17,8	56,0
Guinea Pig 400 g	0,08	0,57	1,0	2,25	2,4	5,2	10,2	31,5
Rabbit 1,5 kg	0,04	0,25	0,44	1,0	1,08	2,4	4,5	14,2
Cat 2 kg	0,03	0,23	0,41	0,92	1,0	2,2	4,1	13,0
Ape 4 kg	0,016	0,11	0,19	0,42	0,45	1,0	1,9	6,1
Dog 12 kg	0,008	0,06	0,10	0,22	0,24	0,52	1,0	3,1
Human 70 kg	0,0026	0,018	0,031	0,07	0,076	0,16	0,32	1,0

KOMITE ETIK PENELITIAN KESEHATAN  
*HEALTH RESEARCH ETHICS COMMITTEE*  
RSUP PROF. DR. R. D. KANDOU MANADO  
*RSUP PROF. DR. R. D. KANDOU MANADO HOSPITAL*

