## Study Protocol with SAP and/or ICF

The study was a 4-week, randomized, double-blind, placebo-controlled clinical trial followed by a 1-week screening period. Participants who respond to the invitation and meet the entry criteria during the telephone screening interview are scheduled for the initial visit. Evaluation during the initial visit includes physical examination in the form of BMI (Body Mass Index) based on Asia-Pacific guidelines and blood parameter screening tests in the form of blood glucose, triglycerides, high-density lipoprotein (HDL), low-density lipoprotein (LDL) and total cholesterol, and PGC-1 $\alpha$  were performed on all participants within 1 week of the initial screening. A random number between 1 and 70 was generated for each subject and registered participants were scheduled for their first visit and randomly assigned to the sea grape extract group (n=35) or placebo (n=35). Sea grape extract/placebo tablets/capsules were given to participants every 1 week

(1 day of consumption per oral) 15 Minutes before eating (According to the diabetes drug guideline consumption).

During the 4-week intervention period, participants were asked to continue their usual diet and not to consume functional foods or other dietary supplements. Anthropometry (BMI), Waist Hip Ratio (WHR), blood parameters, urine profile (Marker of toxicity), and nutrient intake of both groups were measured before and after the intervention period. During the trial phase, all participants were instructed to maintain their normal diet and physical activity. Each week participants were asked to report assessments of side effects or changes in training, lifestyle, or diet; and to evaluate tablet compliance.

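### The analysis plan names no baseline covariate and no target contrast, although every blood marker is measured at week 0; adjusting for that value would sharpen the week-4 comparison

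*Combined protocol and SAP*

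**What the plan says.** The analysis plan is the short Statistical Analysis section. It gives the software, the model sentence "Fixed effects include treatment groups, treatment visits, and interactions between treatment and visit groups", and the rule that p < 0.05 "is considered statistically significant". It does not name a baseline covariate, a target visit or contrast, or a within-participant covariance. It also leaves open whether week 0 counts as one of the model's visits.

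Baseline values are planned for every marker. Measurement of Efficacy Results schedules one fasting draw at screening and three more, which it describes thus: "well as in the 0, 2nd and 4th weeks of the intervention period to obtain blood glucose profiles, total cholesterol, triglycerides". The same sentence goes on to HDL, LDL and PGC-1α. The section headed Study Protocol with SAP and/or ICF adds that "blood parameters, urine profile (Marker of toxicity), and nutrient intake of both groups were measured before and after the intervention period". No other section says how the baseline value enters the analysis.

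**The concern.** The list of terms may not be exhaustive, but nothing elsewhere completes it. An analyst could follow the plan in at least three ways:

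- **Week-4 levels.** The arms are compared at week 4 and the week-0 value is not used.
- **Change or interaction.** Week 0 is a model visit, and the treatment effect is the week-4 minus week-0 difference between arms, or the overall group-by-visit test. Baseline is used, but with its slope in effect fixed at 1.
- **Group main effect.** The arm difference is averaged over visits. If week 0 is included, a visit with no treatment effect dilutes the estimate.

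The first two are valid under randomisation but give away precision that the planned data could supply. The third estimates a weaker quantity. With 35 men per arm and no sample-size justification, precision matters. An overall interaction test also gives no single estimate to report.

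**Working it through.** **Inputs from the documents:** 35 men per arm; blood at weeks 0, 2 and 4; significance at 0.05 (two-sided assumed, as sidedness is not stated). The plan has no power or precision figure to reproduce.

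**Assumptions:** week-0 to week-4 correlation ρ = 0.3, 0.5, 0.7, 0.8; equal SDs at all visits (SD = 1); effect 0.5 SD at week 4; no dropout.

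**1. Variance of the week-4 comparison, relative to comparing week-4 levels (= 1)**

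- Change score: 2(1 − ρ).
- Week-0 covariate: (1 − ρ²) × (1 + 1/66). The second factor, about 1.5%, is the cost of estimating the slope with 70 men.

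At ρ = 0.7, for example, change is 2 × 0.3 = 0.600 and the covariate analysis is 0.51 × 1.0152 = 0.518. The reduction is 1 − 0.518 = 48% against levels and 1 − 0.518/0.600 = 14% against change.

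**2. Interval and power.** The 95% half-width is t(0.975, df) × √(variance × 2/35), with 68 df for levels and change and 67 df for the covariate. Power is from the noncentral t distribution.

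| | ρ = 0.3 | 0.5 | 0.7 | 0.8 |
|---|---|---|---|---|
| Variance, change | 1.400 | 1.000 | 0.600 | 0.400 |
| Variance, adjusted | 0.924 | 0.761 | 0.518 | 0.365 |
| Reduction against levels | 8% | 24% | 48% | 63% |
| Reduction against change | 34% | 24% | 14% | 9% |
| Half-width, levels (SD) | 0.477 | 0.477 | 0.477 | 0.477 |
| Half-width, change (SD) | 0.564 | 0.477 | 0.369 | 0.302 |
| Half-width, adjusted (SD) | 0.459 | 0.416 | 0.343 | 0.288 |
| Power, levels | 54.1% | 54.1% | 54.1% | 54.1% |
| Power, change | 41.4% | 54.1% | 75.9% | 90.3% |
| Power, adjusted | 57.3% | 65.6% | 81.7% | 92.6% |
| Men per arm for levels to match adjusted | 37.9 | 46.0 | 67.6 | 95.8 |
| Men per arm for change to match adjusted | 53.0 | 46.0 | 40.6 | 38.3 |

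**3. The overall group-by-visit test (2 df).** With weeks 0, 2 and 4 as responses and a participant term (compound symmetry), λ = (35/2) × Σ(d_t − mean d)²/(1 − ρ), referred to noncentral F(2, 136). The like-for-like comparator is a 2-df test of weeks 2 and 4 adjusted for week 0, on F(2, 66).

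| Effect at weeks 0/2/4 (SD) | Test | ρ = 0.3 | 0.5 | 0.7 | 0.8 |
|---|---|---|---|---|---|
| 0/0.5/0.5 | Interaction | 42% | 56% | 79% | 93% |
| 0/0.5/0.5 | Adjusted | 68% | 73% | 87% | 95% |
| 0/0.25/0.5 | Interaction | 33% | 44% | 66% | 84% |
| 0/0.25/0.5 | Adjusted | 49% | 56% | 73% | 87% |

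Simulation of 40,000 trials per setting agrees with the calculated change, covariate, interaction and adjusted 2-df powers to within 0.6 percentage points. Null rejection was 4.8% to 5.1%.

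**4. The group main effect with week 0 averaged in.** For effects 0/0.5/0.5 the averaged effect is (0 + 0.5 + 0.5)/3 = 0.333 SD, and the relative variance is (1 + 2ρ)/3. Power on 68 df is 46.9/39.1/33.6/31.5%.

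**5. When adjustment does not pay.**

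- Against levels, it breaks even at ρ = √(1/67) = 0.12. At ρ = 0, power falls from 54.1% to 53.4%.
- Against change, it breaks even where (1 + ρ) × (1 + 1/66) = 2, that is at ρ = 0.97.

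**The case against.** The strongest reply is that the natural reading of a group, visit and group-by-visit model has week 0 as a visit and the interaction as the treatment test. That is a common, valid analysis and it already uses baseline. The most striking figures (63% less variance, 54% against 93% power, 96 men per arm) arise only if week-4 levels are compared, which no section says. Against the change contrast the half-width narrows by 19% at ρ = 0.3 and 13% at 0.5, but by only 7% at 0.7, 4% at 0.8 and under 2% at 0.9.

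The power gains also depend on the assumed 0.5 SD. At 0.67 SD and ρ = 0.7, change has 94.6% and adjustment 97.0%; at 0.8 SD these are 98.9% and 99.6%.

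All of this stands as a limit on size. It does not remove the point. The plan does not exclude the week-4 level comparison or the diluted main effect. The documents give no correlation from which to argue that the loss is small. Six blood markers may also have different correlations: levels lose most when ρ is high and change loses most when ρ is low, so neither is a safe choice for all six.

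One further caution is fair. Subjects/Participants already reports the 70 eligible men and their mean age, so the text was written at least partly after screening. If outcomes had been seen by group, a new model would need to be labelled post hoc.

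**Conclusion.** The concern holds. The plan leaves the treatment contrast unnamed and does not adjust for a baseline value collected for every blood marker. The consequence is lost precision, not bias, except that a main effect averaged over week 0 would also dilute the estimate.

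For ρ from 0.3 to 0.8, adjustment lowers the variance of the week-4 difference by 8% to 63% against week-4 levels and by 34% down to 9% against change. At ρ = 0.5 both reductions are 24%. Against the overall interaction test the gain is 26 or 16 percentage points of power at ρ = 0.3 (constant or linear effect) and 2 to 3 points at ρ = 0.8.

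These sizes rest on the assumed correlations, equal SDs and no dropout; the power figures also rest on the 0.5 SD effect. The documents cannot narrow the range. The change should be made because it costs almost nothing, but the trial is not invalid without it.

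**What to change.** For each blood marker, specify a repeated-measures model with weeks 2 and 4 as responses and these terms: treatment, visit, treatment-by-visit, the week-0 value and week-0-by-visit. Name the within-participant covariance, for example unstructured. Declare the adjusted week-4 difference between arms, with its 95% CI, as the treatment effect. An acceptable alternative keeps week 0 as a response with a common baseline mean in both arms; it has the same large-sample variance, 1 − ρ². State that week 0 is the baseline, and whether the screening draw plays any part.

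The cost is a few sentences in the plan and a few lines of SPSS MIXED code, with no extra data, visits or participants. In the week-4 comparison the covariate takes one degree of freedom, with a worst-case power loss of 0.7 points against week-4 levels (at ρ = 0). If outcome data have already been examined by group, report the new model as post hoc alongside the model in the plan.

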Sea grape (*Caulerpa racemosa*) or lawi-lawi (local Indonesian term) is a species of green algae classified as *Caulerpaceae* family that had be found in the waters around Sulawesi (Pakki et al., 2020). Sea grapes are harvested intensively because they are an important source of macronutrients and micronutrients, especially in East and Southeast Asia (commercially grown in ponds and consumed in parts of the Philippines, Indonesia and Vietnam) as the main source of traditional diets (Chen et al., 2019), although it is still used for health products. Several studies have shown that sea grapes contain several bioactive components, such as protein, polysaccharides, polyphenols, flavonoids, and antioxidants (P. Yang et al., 2015; Yep et al., 2019; Taslim & Fahrul, 2021). In addition, sea grapes contain high antioxidant levels, and may be potential as functional foods or nutraceuticals (Tanna et al., 2020; Yep et al., 2019; Nurkolis et al., 2021). Doses of 150 mg/kg BW (30 mg/200g BW) sea grape extract in a previous pre-clinical trial, showed that it could improve blood glucose, total cholesterol and serum PGC-1 levels in rats fed a diet high in fat and cholesterol (Kuswari et al., 2021). In addition, you also have hepatoprotective activity (aka non-toxic) in diabetic mice (Qudus B Aroyehun et al., 2020). Previous research (Kuswari et al., 2021), is an in vivo (Pre-clinical) study that has not represented the benefits or efficacy of sea grape extract on variables tested in humans. Therefore, this clinical trial was conducted to support the effect of sea grape extract-antioxidant on blood glucose, total cholesterol, and PGC-1 levels in obese men for 4 weeks using a Randomized-Double Blind Controlled Trial.

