### **Subjects/Participants**

The study participants were recruited during 2021 at RSUP [name]. RD. Kandou (Manado, Republic of Indonesia). A total of 150 participants agreed to participate in the study. Only individuals men who are obese ( $BMI \geq 25 \text{ kg m}^{-2}$  and Waist Hip Ratio (WHR)  $\geq 0.90$ ) according to Asia-Pacific guidelines and have not been diagnosed with other diseases were included in the study. To meet guidelines for evaluating the efficacy of functional food referring to the Korea Food and Drug Administration (because Indonesia does not yet exist and Korea belong to one Asian region so used) (KFDA Guideline, 2021), very obese participants ( $BMI \geq 30 \text{ kg m}^{-2}$ ) were not included in the study.

In total, 70 participants met the research criteria (age  $29.98 \pm 3.26$  year; weight,  $\dots \pm \dots$  kg; BMI,  $\dots \pm \dots \text{ kg m}^{-2}$ ) and were randomly divided into two groups ( $n = 35$  each) given sea grape extract  $1.68 \text{ g}/70\text{kg BB day}^{-1}$  or placebo ( $1.68 \text{ g}/70\text{kg BB day}^{-1}$ ). The exclusion criteria for this study are as follows: (a) significant weight variation (over 10%) in the last 3 months; (b) a history of cardiovascular disease including arrhythmia, heart failure, or myocardial infarction, diabetes

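### Three unranked objective outcomes are each judged at p<0.05 with no primary outcome, deciding contrast or multiplicity rule; if any one may carry the efficacy conclusion, the false-positive chance is up to about 14% rather than 5%

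*Combined protocol and SAP*

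**What the plan says.** The Introduction states the aim as the effect of the extract "on blood glucose, total cholesterol, and PGC-1 levels in obese men for 4 weeks". The three outcomes stand side by side, with no order of importance.

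The Statistical Analysis section names the software, a model and a threshold. On the model: "Fixed effects include treatment groups, treatment visits, and interactions between treatment and visit groups". On the threshold: p<0.05 "is considered statistically significant". It does not say which term, or which visit, decides whether the extract worked.

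Timing is described in two ways. The section Study Protocol with SAP and/or ICF says that "blood parameters, urine profile (Marker of toxicity), and nutrient intake of both groups were measured before and after the intervention period". Measurement of Efficacy Results gives more sampling times: "Blood samples were collected after a minimum of 12 hours of fasting during initial screening as" and, continuing, "well as in the 0, 2nd and 4th weeks of the intervention period to obtain blood glucose profiles, total cholesterol, triglycerides". The same section lists the full blood panel as "blood glucose, total cholesterol, triglycerides, high-density lipoprotein (HDL), low-density lipoprotein (LDL) and PGC-1", so three further blood outcomes sit beside the three objectives.

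Subjects/Participants reports allocation as already done: the 70 men met the criteria "and were randomly divided into two groups" of 35.

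**The concern.** A p<0.05 rule limits the false-positive chance to 5% for one test named in advance. Here three objectives are open, and the plan does not say how their results combine into a conclusion about the extract. If the extract does nothing and the report may rest on whichever objective reaches significance, the chance of a false finding exceeds 5%. The choice of objective could also be made after the results are known.

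The comparison itself is not fixed either. The treatment term and the treatment-by-visit term test different hypotheses. There are two possible baselines (screening and week 0) and two post-baseline visits (weeks 2 and 4).

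**Working it through.** **Inputs from the documents.** Three objective outcomes (Introduction); threshold 0.05 per test (Statistical Analysis); 35 men per group (Study Protocol with SAP and/or ICF; Subjects/Participants). The documents state no overall error rate, power or sample-size derivation, so there is no figure of the plan's own to reproduce.

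**Assumptions.** The documents do not give sidedness, so tests are taken as two-sided at 5%, which is 2.5% in the direction of benefit. They give no between-outcome correlation, so 0, 0.3, 0.5 and 0.7 are shown. There is no true effect on any outcome and one test per outcome.

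**Step 1: independent outcomes.**
- At least one difference in either direction: 1 − 0.95³ = 1 − 0.8574 = 14.26%.
- At least one false benefit: 1 − 0.975³ = 1 − 0.9269 = 7.31%.

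**Step 2: correlated outcomes.** For equicorrelated normal statistics with correlation ρ and c = 1.96, the either-direction rate is 1 − ∫ φ(u) [Φ((c − √ρ·u)/√(1−ρ)) − Φ((−c − √ρ·u)/√(1−ρ))]³ du. The benefit rate uses only the upper limit, Φ((c − √ρ·u)/√(1−ρ))³. The Holm row uses the first-step threshold 0.05/3 = 0.0167.

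| Correlation | 0 | 0.3 | 0.5 | 0.7 | Single test |
|---|---|---|---|---|---|
| Any difference, each at 0.05 | 14.26% | 13.62% | 12.54% | 10.92% | 5% |
| Benefit, each at 0.05 | 7.31% | 6.83% | 6.27% | 5.46% | 2.5% |
| Any difference, Holm | 4.92% | 4.76% | 4.45% | 3.92% | – |
| Benefit, Holm | 2.48% | 2.38% | 2.23% | 1.96% | – |

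For jointly normal two-sided tests, 14.26% is the maximum at any correlation (Sidak inequality). The benefit rate cannot exceed 3 × 2.5% = 7.5% (Bonferroni). Simulated t-tests with 35 per group and independent outcomes gave 14.2% and 7.2%.

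**Step 3: sensitivity to the visit.** If either the week-2 or the week-4 baseline-adjusted comparison could carry the claim, simulation gives 25.9 / 24.6 / 22.9 / 20.2% for any difference at the four correlations. This assumes a within-subject correlation of 0.6.

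**Step 4: contrast chosen after unblinding.** If the raw, change-from-baseline and baseline-adjusted week-4 versions are all left open (same 0.6), the Holm first step across three outcomes gives about 10.2 / 9.8 / 9.2 / 8.0%, not 5%.

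**Step 5: price of Holm.** The effect detectable with 80% power at 35 per group, by two-sample t-test, is 0.679 SD at 0.05 and 0.790 SD at 0.0167. The normal approximation is close: (1.960 + 0.842) × √(2/35) = 0.670, and (2.394 + 0.842) × √(2/35) = 0.773. Adjusting for a baseline correlated 0.6 with week 4 multiplies by √(1 − 0.36) = 0.8, giving 0.543 and 0.632. Allowing for the estimated slope gives 0.548 and 0.637. At correlation 0.4 the pair is 0.627 and 0.730; at 0.8 it is 0.411 and 0.478.

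**The case against.** The strongest objection is that no sentence adopts an any-one-wins rule. The plan only says when a result counts as significant. If each outcome supports only its own claim, about glucose or about cholesterol, each claim keeps its 5%. If all three had to succeed, the joint error would be no more than 5%. This stands: a reader might infer that the plan lets one significant objective prove efficacy, but the documents are silent on the rule. The 14% therefore applies to one permitted reading, not to a stated rule.

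The time point is also less open than the sampling schedule suggests. A four-week objective and blood measured before and after the intervention both point to week 4, and an interim week-2 sample is not by itself a rival endpoint. This stands in part, because no sentence fixes the contrast. A reader might take the 20–26% from Step 3 as the plan's error rate. It is not: it needs a choice between visits that the plan does not describe. Nor should a false-benefit rate be attached to the treatment-by-visit term. Across three visits that is a two-degree-of-freedom F test, which has no direction.

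Finally, this is a small trial following rat data and might be meant as exploratory. The available text does not say so. The Introduction presents the trial as support for an effect, and the measurements are headed as efficacy results.

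**Conclusion.** The concern holds as an omission. The available text gives three unranked objectives, a 0.05 threshold and no rule linking them to a conclusion.

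If a significant result on any one objective may support efficacy, an inert extract yields at least one false difference with probability 14.3% to 10.9% instead of 5%. It yields a false benefit with probability 7.3% to 5.5% instead of 2.5%. In the beneficial direction that is about 2.5 to 3 times the single-test rate for correlations from 0.5 down to 0 (6.27/2.5 = 2.5; 7.31/2.5 = 2.9).

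These figures rest on two-sided testing, one test per outcome, no true effect and assumed correlations. They do not apply to separately stated single-outcome claims. The gap should be closed before any result is presented as evidence that the extract works.

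**What to change.** State in the SAP, with a date, one contrast for every outcome: the between-group difference at week 4, adjusted for the week-0 value. Estimate it from the planned model (group, visit, group-by-visit) with weeks 2 and 4 as outcome visits. Then:

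- **If no one has seen unblinded data**, either (1) name one of glucose, total cholesterol or PGC-1 as primary and test the other two in a stated fixed order, each at two-sided 5% and only if the previous test is significant; or (2) apply Holm across the three at an overall two-sided 5%.
- **If data are already unblinded**, apply Holm to this contrast, label both the contrast and the adjustment post hoc, and do not claim 5% control. Because randomisation is reported in the past tense, the sponsor should state which situation applies.

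Label week-2 results and all other outcomes secondary or exploratory, and report them with 95% confidence intervals.

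The change is to wording only; no visits, samples or participants are added. A fixed order costs no power on the primary outcome. Holm's first step raises the effect detectable with 80% power from 0.68 to 0.79 SD unadjusted, or from about 0.54–0.55 to 0.63–0.64 SD with baseline adjustment at an assumed correlation of 0.6.
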